**Statistical Methods:**

**Sample Size Calculation and Statistical Power:**

Approximately 247 patients **CCI**

**Analysis Populations:**

The intent-to-treat (ITT) population will consist of all patients who are randomized in the study with confirmed SARS-CoV2 infection under protocol version 6.0 and above, regardless of whether or not they receive study treatment.

The all-treat (AT) population will consist of all patients who took at least one dose of study treatment on this study and have confirmed SARS-CoV2 infection.

**Efficacy Analyses:**

The difference of the primary endpoint (Day 14 OSI) between treatment arms will be calculated with a 95% confidence interval (CI). Comparison of OSI rates between the 2 treatment arms will be performed using the Cochran-Mantel-Haenszel (CMH) test stratified by the randomization stratification factors. The CMH estimate of the odds ratio and its 95% CI and the p-value for testing the treatment difference will be reported.

Analyses of other efficacy endpoints will be specified in [Section 9.4.1](#) and the SAP.

**Safety Analyses:**

Safety analyses will be based on the reported AEs and other safety information, such as 12-lead electrocardiogram (ECG), clinical laboratory assessments including hematology, serum chemistry, vital signs and physical examination.

Safety analyses will be performed using the AT population.

**SCHEDULE OF ASSESSMENTS**

**Table 1: Schedule of Assessments for admitted patients only**

| Activity/Assessment                            | Screening  | Dosing Period                     |           |           |           |            |            |             |             |            |            | End-of-Treatment | Hospital Discharge | Safety Follow-Up / End of Study  |
|--|------------|-----------------------------------|-----------|-----------|-----------|------------|------------|-------------|-------------|------------|------------|------------------|--------------------|--|
|  | D -2 to D1 | D1 ±1 day                         | D3 ±1 day | D5 ±1 day | D8 ±1 day | D10 ±1 day | D12 ±1 day | D 15 ±1 day | D 19 ±1 day | D22 ±1 day | D26 ±1 day | D14/28*          |                    |  |
| Informed Consent b                  | X          |                                   |           |           |           |            |            |             |             |            |            |                  |                    |  |
| Inclusion/Exclusion                            | X          |                                   |           |           |           |            |            |             |             |            |            |                  |                    |  |
| Demographics                                   | X          |                                   |           |           |           |            |            |             |             |            |            |                  |                    |  |
| Medical history                                | X          |                                   |           |           |           |            |            |             |             |            |            |                  |                    |  |
| Disease History                                | X          |                                   |           |           |           |            |            |             |             |            |            |                  |                    |  |
| Vital signs c                       | X          | Twice daily during Hospital Stay  |           |           |           |            |            |             |             |            |            |                  |                    |  |
| Complete Physical Exam                         | X          |                                   |           |           |           |            |            |             |             |            |            |                  | X                  |  |
| Pregnancy testing (per site guideline)         | X          |                                   |           |           |           |            |            |             |             |            |            | X                |                    |  |
| Ordinal Score d                     | X          | Daily and the day after discharge |           |           |           |            |            |             |             |            |            |                  | X                  |  |
| 12-lead ECG e                       | X          | As clinically indicated           |           |           |           |            |            |             |             |            |            |                  |                    |  |
| ABG (Arterial Blood Gas) f          | X          | As clinically indicated           |           |           |           |            |            |             |             |            |            |                  |                    |  |
| CBC with differential                          | X          | X                                 | X         | X         | X         |            | X          | X           | X           | X          | X          |                  | X                  |  |
| PT, aPTT, INR                                  | X          | X                                 | X         | X         | X         |            | X          | X           |             | X          | X          |                  |                    |  |
| Complete serum chemistry                       | X          | X                                 | X         | X         | X         |            | X          | X           | X           | X          | X          |                  | X                  |  |
| C-reactive protein, Ferritin, LDH g | X          | X                                 | X         | X         | X         |            | X          | X           | X           | X          | X          |                  |                    |  |
| CCI  |            |                                   |           |           |           |            |            |             |             |            |            |                  |                    |  |

|  |   |                     |   |   |   |   |                |     |     |     |     |   |  |   |
|--|---|---------------------|---|---|---|---|----------------|-----|-----|-----|-----|---|--|---|
| Cells for Leukocyte Phenotyping f             | X | X                   |   |   | X |   | X g | X   |     |     |     |   |  |   |
| Selinexor or Placebo k                        |   | X                   | X | X | X | X | X              | (X) | (X) | (X) | (X) |   |  |   |
| Blood draws for selinexor PK h                |   | X                   | X | X |   |   |                |     |     |     |     |   |  |   |
| Cytokines  | X |                     | X | X | X |   |                |     |     |     |     |   |  |   |
| Adverse Events (any)                                     | X | Recorded Throughout |   |   |   |   |                |     |     |     |     | X |  | X |
| Concomitant Medications                                  | X | Recorded Throughout |   |   |   |   |                |     |     |     |     | X |  |   |
| 5-HT3 antagonists Ondansetron or equivalent i |   | Daily as needed     |   |   |   |   |                |     |     |     |     |   |  |   |
| Survival Follow-up                                       |   |                     |   |   |   |   |                |     |     |     |     |   |  | X |

a Patients will remain on therapy for up to 14 days (or 28 days based on treating physician discretion)

b Refer to [Section 10.1](#) for Informed Consent

c Vital signs include respiratory rate, temperature, and oxygen saturation It is recommended to measure SpO2 in the same position for each patient throughout the duration of the study

d Ordinal Score ([Section 7.3.2](#)) will be assessed at first assessment of day

e For patients who had an ECG during the hospitalization, the ECG does not need to be repeated. Results of this most recent ECG should entered into the eCRF

f Required study and should be performed unless hospital SOP does not permit or if not feasible, to be performed locally as available. Once 2 negative viral assessments are documented testing can be stopped.

g Day 12 or Day 15

h Blood samples (~2mL) for selinexor PK will be collected at 4 ± 1 hr, 24 ± 4 hrs post selinexor dose on Day 1 and predose on Day 3 and Day 5. Details for PK sample collection and processing can be found in the Laboratory Manual.

i This visit will occur 30 (+2) days post end of treatment and may be performed as either a telephone call or an in-clinic visit. Only follow up on SAEs will be reported.

j In order to minimize nausea, all patients should receive ondansetron 8 mg or equivalent unless contraindicated, starting on Day 1 before the first dose of selinexor and continued 2-3 times daily thereafter, as needed. Alternative antiemetic agents may be used if the patient does not tolerate or has inadequate antiemetic effect with 5-HT3 antagonists.

k It is recommended that patients are dosed with study drug within 12 hours of consent

l If feasible.

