**Table 2: Schedule of Assessment Post-Discharge Period for Outpatients Only**

| Activity/Assessment a                                | Schedule                                      | Day 28 | End of Study b |
|---|---|--------|---------------------------|
| Follow-up Call  | Weekly until day 28                           |        | X                         |
| Ordinal Score   | On Day 7 and 14                               |        |                           |
| Adverse Event   | Weekly until day 28                           |        | X                         |
| Study Drug Administration c                          | Dosing Days 1, 3, 5 of each week until day 28 |        |                           |
| CBC with differential and Complete Serum Chemistry c | Twice weekly until 14 or day 28               |        |                           |
| CCI  |   |        |                           |
| Survival Follow-up  |   | X      |                           |

a Sponsor Risk Management Plan for Conduct of Clinical Trials outlines procedures to be conducted during the COVID-19 pandemic.

b This visit will occur 30 (+2) days post end of treatment, and may be performed as either a telephone call or an in clinic visit. Only follow on SAEs will be reported.

c Only for patients who are discharged on study treatment and while on study treatment. Decision to continue beyond day 14 is per protocol guidelines

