### **8.1.2. Recording of Adverse Events**

All AEs that begin or worsen after the patient has provided informed consent will be recorded. Those AEs that occur prior to study dosing, can be captured in the patient's baseline conditions, however if any of these AEs are considered, serious, these are to be reported both to Pharmacovigilance and documented in the eCRF AE log. For events that are considered by the Investigator to be related to the study drug, the monitoring of the AE should be continued through the end of the study, for at least 30 days following last dose of study drug (if the end of the study is within 30 days of the last dose of study drug), or until the AE has resolved.

Investigators should use medical judgment in determining whether a particular symptom or sign is considered to be a part of COVID-19 infection clinical course or not and report them or not as AEs according to such determination. When a clear determination cannot be made by the investigators, a sign or symptom should be reported as AEs. All deaths irrespective of cause of death including due to COVID-19 during the study should be reported to the Sponsor using an SAE form.

Adverse events (including laboratory abnormalities that constitute AEs) should be described using a diagnosis whenever possible, rather than individual underlying signs and symptoms. When a clear diagnosis cannot be identified, each sign or symptom should be recorded as a separate AE.

The Investigator should ask the patient non-leading questions to determine if any AEs have occurred during the study, since the last study visit. Adverse events may also be recorded when they are volunteered by the patient, or through physical examination, laboratory tests, or other clinical assessments.

An AE should be followed until its resolution or until it is judged to be permanent, and assessment should be made at each visit (or more frequently, if necessary) of any changes in severity of the event, the suspected relationship to the study treatment, the interventions required to treat the event, and the outcome.

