#### **9.4.2. Safety Analyses**

Safety analyses will be based on the reported AEs and other clinical information.

Safety analyses will be performed in AT population.

The safety and tolerability of selinexor will be evaluated by means of drug-related AE reports, physical examinations, and laboratory safety evaluations. The grading of the severity of the AEs will be done according to CTCAE, v.5.0. Investigators will provide their assessment as either the AE is related or not related to study drug.

Treatment-emergent AEs, SAEs, AEs of at least Grade 3 in severity, related AEs, and AEs leading to withdrawal of treatment will be summarized by cohort and in the overall safety population. Treatment-emergent AEs will be those that start or worsen on or after the first day of study treatment, through 30 days after last dose. Related AEs will be those with an Investigator determination of related to study drug.

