### **8.1 Adverse Events**

Adverse events (AEs) will be coded using the most recent version of MedDRA.

The severity of all AEs will be graded according to the NCI CTCAE Grading Scale, v. 5.0. An AE with a CTCAE grade of 3 or higher is considered a severe AE. The severity of the AE is different from the seriousness of the AE. For AEs not covered by CTCAE, the severity will be characterized as “mild,” “moderate,” “severe”, “life-threatening” (corresponding to Grades 1 to 4). Handling rules for missing severity of AEs are described in Section 4.4.3.

Treatment emergent adverse events (TEAEs) are defined as those AEs that develop or worsen after the first dose of study treatment and up to 30 days beyond the last dose of study treatment. Additionally, any AEs that occurred 30 days after the last dose of study treatment will also be considered as TEAE, if assessed by the Investigator as related to study treatment.

AEs are classified as related or not related to study treatment. Any AEs with missing or unknown relationship will be considered as related to study treatment.

All summaries of AEs described in this section will be on TEAEs. All summaries will be ordered by decreasing frequency of total number of patients in overall in PT within SOC which is sorted alphabetically. In the case of equal frequency of number of patients in PTs, then summaries of AEs will be sort alphabetically.

An overall summary for AEs including number of patients who experience an TEAE will be provided:

- TEAEs
- Grade 3/4 TEAEs
- Serious TEAEs
- TEAEs leading to study treatment discontinuation
- TEAEs leading to dose reduction of study treatment
- TEAEs leading to dose interruption of study treatment
- TEAEs leading to death
- Treatment-related TEAEs
- Treatment-related serious TEAEs

- Treatment-related TEAEs leading to study treatment discontinuation
- Treatment-related TEAEs leading to dose reduction of study treatment
- Treatment-related TEAEs leading to dose interruption of study treatment
- Treatment-related TEAEs leading to death

The following types of TEAEs will be summarized by primary SOC and PT:

- All TEAEs
- All TEAEs, by causality
- All TEAEs, by maximum grade
- Grade  $\geq 3$  TEAEs
- Grade  $\geq 3$  TEAEs, by causality
- TEAEs leading to study treatment discontinuation
- TEAEs leading to dose reduction of study treatment
- TEAEs leading to dose interruption of study treatment
- TEAEs leading to death
- Serious TEAEs
- Serious TEAEs, by causality

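### TEAEs are counted to 30 days after last dose, but after discharge no scheduled contact beyond Day 28 is clearly designated to collect new non-serious AEs

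*Protocol*

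**What the plan says.** **Analysis window.** Protocol Section 9.4.2 counts TEAEs "through 30 days after last dose". SAP Section 8.1 does the same, "up to 30 days beyond the last dose of study treatment", and adds later events if the investigator judges them related. Neither limits the window to serious events.

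**Collection after discharge.** Protocol Table 2 schedules AE collection "Weekly until day 28", with a further mark at End of Study.

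**The last contact.** Table 1 footnote i sets its timing: "This visit will occur 30 (+2) days post end of treatment". The same footnote sets its content: "Only follow up on SAEs will be reported". For discharged patients the governing text is Table 2 footnote b: "Only follow on SAEs will be reported".

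**Text that points the other way.** The Table 1 AE row, whose label opens "Adverse Events (any", is marked in the Safety Follow-Up / End of Study column, and the Table 2 AE row is marked at End of Study. Protocol Section 8.1.2 states: "All AEs that begin or worsen after the patient has provided informed consent will be recorded". It gives no stop date, has the investigator ask about events since the last visit, and keeps treatment-related events under monitoring for at least 30 days after the last dose.

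**A third time frame.** The safety objective (Protocol Section 2 and SAP Table 1) gives up to 28 days.

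**The concern.** The TEAE tables will carry a 30-day post-dose label. A site that follows the schedule footnotes has no scheduled occasion after Day 28 to ask a discharged patient about new non-serious events. An event that nobody asks about is counted as no event, so incidence under that label can be too low.

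Three features make this more than a wording slip.

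- **Severity.** Protocol Section 8.1.2.1 says that a Grade 3 or 4 event is not automatically an SAE. Non-serious events of Grade 3 or higher are therefore exposed, and SAP Section 8.1 tabulates Grade 3 or higher TEAEs and TEAEs by maximum grade.
- **No laboratory backstop.** Under Table 2 footnote c, post-discharge blood counts and chemistry are done only while the patient is on study treatment. Once dosing ends, detection of non-serious events relies on the calls.
- **Site variation.** Protocol Section 7 sends sites to the schedule of assessments for procedures and timing. With about 40 sites planned (Synopsis), some may follow the AE row and others the footnote.

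**Working it through.** The documents state no figure for this gap, so there is none to reproduce. The check is a day count followed by a comparison of the texts.

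**Inputs**
- Day 1 is the date of first study treatment (SAP Section 4.2).
- The TEAE window ends 30 days after last dose (Protocol 9.4.2, SAP 8.1).
- The last post-discharge AE call before the final contact is taken as Day 28 (Table 2).
- The last scheduled dose is Day 12 for the 2-week course (Table 1) and Day 26 for the extension (Protocol 3.1).
- The final contact is taken to follow the footnotes, that is, SAEs only.

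**Formulas**, for a last dose on Day L:
- window end = L + 30
- uncovered days = (L + 30) − 28 = L + 2
- share of post-dose window = (L + 2) / 30
- share of whole TEAE period = (L + 2) / (L + 30)

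| Last dose | Window ends | Uncovered days | Share of 30 post-dose days | Share of whole TEAE period |
|---|---|---|---|---|
| Day 1 | Day 31 | 29–31 (3) | 3/30 = 10.0% | 3/31 = 9.7% |
| Day 5 | Day 35 | 29–35 (7) | 7/30 = 23.3% | 7/35 = 20.0% |
| Day 8 | Day 38 | 29–38 (10) | 10/30 = 33.3% | 10/38 = 26.3% |
| Day 12 (2-week course) | Day 42 | 29–42 (14) | 14/30 = 46.7% | 14/42 = 33.3% |
| Day 13 | Day 43 | 29–43 (15) | 15/30 = 50.0% | 15/43 = 34.9% |
| Day 26 (4-week course) | Day 56 | 29–56 (28) | 28/30 = 93.3% | 28/56 = 50.0% |

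Half of the post-dose window is reached when L + 2 ≥ 15, that is, for a last dose on Day 13 or later. If the 30 days are counted from the Day 14 end-of-treatment visit instead, the 2-week figure is (44 − 28)/30 = 16/30 = 53.3%.

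**What the final contact collects, source by source**

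| Source | Scope at the final contact |
|---|---|
| Table 1 footnote i; Table 2 footnote b | SAEs only |
| AE row, Table 1 | any AE |
| AE row, Table 2 | AEs, with no limit stated in the row |
| Section 8.1.2 | all AEs after consent, no stop date |
| Sections 8.2.1.2 and 8.2.1.3 | SAEs, explicitly to at least 30 days after treatment stops |

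SAEs have an explicit 30-day collection rule. New non-serious events have only the general rule in 8.1.2, and the footnotes contradict it.

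**The case against.** The strongest reply is that Section 8.1.2 governs AE recording. It has no end date, it is not limited to serious events, and both AE rows are marked at the final contact. This stands in part. A reader might infer from the footnotes that non-serious events are simply not collected after Day 28. The documents do not support that; they show conflicting instructions. But the reply does not remove the problem, because the footnotes are the specific instruction for that contact.

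A reader might also infer that half or more of the window is always lost. That fails for the 2-week course ending on Day 12 (47%) and more clearly for early stoppers. The 93% figure applies only to patients dosed to Day 26, and the documents do not say how many there would be.

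A third inference is bias between arms: the gap grows with treatment duration, and continuation depends on tolerability and clinical course. This is a possibility only. Both arms follow the same schedule, and nothing in the documents allows an estimate.

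Two further points for the plan stand. SAEs and deaths are reportable to at least 30 days after treatment, so those tables are sound. The Day 28 calls also cover the safety objective's own 28-day time frame, although that time frame disagrees with the TEAE definition.

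**Conclusion.** The point holds as an internal contradiction with a practical consequence. The TEAE window runs past Day 28, and for discharged patients no later scheduled contact is clearly designated for new non-serious AEs. If sites follow the footnotes, the uncovered part is 14 of 30 post-dose days (47%) for a last dose on Day 12 and 28 of 30 (93%) for a last dose on Day 26. It falls to 3 of 30 (10%) for a last dose on Day 1.

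These figures assume a patient discharged before Day 28, a last weekly call on Day 28, and no spontaneous reports afterwards. They measure uncovered time, not missed events; the documents give no basis for an event count. The risk is under-counting of non-serious TEAEs and uneven capture across sites. The primary efficacy analysis and the SAE and death tables are not touched.

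**What to change.** Amend Table 1 footnote i and Table 2 footnote b so that all AEs since the last contact, with onset dates, are recorded at the 30 (+2)-day contact. This brings the footnotes into line with the AE rows, Section 8.1.2, Section 9.4.2 and SAP Section 8.1. Reconcile the 28-day time frame in the safety objective (Protocol Synopsis and Section 2, SAP Table 1) with the TEAE window.

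The contact falls at or just after the end of the window, so no visit is added. The cost is a few more questions in an existing call and the text changes. One limit remains: patients would be recalling at least 42 − 28 = 14 days after a Day 12 last dose, and at least 56 − 28 = 28 days after a Day 26 last dose.

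Ending the non-serious TEAE window at Day 28 instead is not advisable. It would discard validly recorded later events, leave 28 − 26 = 2 post-dose days after a Day 26 dose, and conflict with Protocol 9.4.2.
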